7.2 Phase 2a Endpoints

The Phase 2a endpoints are the following:

- Time to reach a NEWS2 score ≤ 2 maintained for at least 24 hours or hospital discharge (whichever comes first) for subjects on active drug versus placebo in the Microbiological Intent-to-Treat (MITT) Population;
- Clinical Improvement or response at TOC for study drug (Day 12) in the MITT Population;
- Proportion of subjects reaching a NEWS2 score ≤ 2 maintained for at least 24 hours or hospital discharge (whichever comes first) for subjects on active drug versus placebo at TOC for study drug (Day 12) in the MITT Population;
- Microbiological outcome at EOT for study drug (Day 5);
- Clinical Improvement or response at TOC for BAT (7 days [± 1 day] after the end of BAT);
- Clinical Improvement or response at EOS (28 days after the end of BAT);
- Time to death;
- NEWS2 score while hospitalized by study day;
- Late composite efficacy, as defined by the following:
 - Survival at EOS (Days 39 to 81); and
 - No evidence of microbiological failure, as defined by either of the following:
 - Blood cultures that remain positive for SA ≥ 7 days from randomization; or
 - Isolation of SA from the blood or another sterile site (eg, joint fluid, tissue) > 14 days from randomization.

- Microbiological failure or relapse by any of the following:
 - Blood cultures that remain positive for SA ≥ 7 days from randomization;
 - Isolation of SA from the blood or another sterile site (eg, joint fluid, tissue) >14 days from randomization; or
 - Blood culture positive for SA >72 hours after the first blood cultures showing CL of SAB (defined as 2 consecutive days with negative SA blood cultures).
- Time to resolution of SAB;
- Time to hospital discharge (and time to hospital discharge readiness);
- Need for and duration of intensive care unit stay;
- Need for and duration of endotracheal mechanical ventilation;
- Need for and duration of noninvasive pressure ventilation (eg, Continuous Positive Airway Pressure, Bilevel Positive Airway Pressure);
- PK of AP-SA02 with IV administration;
- Relationship between AP-SA02 exposures and safety and efficacy endpoints;
- Immunogenicity of AP-SA02 at EOS;
- Time to resolution of any signs and/or symptoms of bacteremia present at Screening;
- Time to resolution of any signs/symptoms related to focal site of SA infection (eg, joint pain; redness; swelling; weight-bearing, back pain; weight-bearing, skin redness; drainage) from randomization on Day 1;

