7.3 Efficacy Outcome Assessments

Clinical outcome will be assessed at TOC for study drug, TOC for BAT, and EOS, and will be based on the definitions in Table 2. The signs and symptoms of SAB include the following:

- Documented temperature $\geq 38.0^{\circ}\text{C}$ (100.4°F) or $\leq 36.0^{\circ}\text{C}$ (96.8°F) measured orally, $\geq 38.5^{\circ}\text{C}$ (101.3°F) or $\leq 36.5^{\circ}\text{C}$ (97.7°F) measured tympanically, or $\geq 39^{\circ}\text{C}$ (102.2°F) or $\leq 37^{\circ}\text{C}$ (98.6°F) measured rectally;
- Heart rate >90 beats per minute;
- Respiratory rate >20 breaths per minute;
- White blood cell count $\geq 12.0 \times 10^9$ cells/L or $\leq 0.4 \times 10^9$ cells/L, or $\geq 10\%$ immature neutrophils;
- Systolic blood pressure <90 mmHg; and/or
- Pain associated with focal site of infection.

Note: On Day 7, the Investigator will provide an assessment of whether additional imaging is needed for potential metastatic infection based on clinical signs/symptoms of SA infection.

Table 2. Definition of Clinical Outcome

Clinical Outcome	Definition
Improvement or response (meets all criteria)	
 • The subject is alive; • Eradication of SAB based on blood cultures obtained through Day 7; • No new metastatic foci including and after Day 7 or complications of SAB; and • Resolution of SAB-related clinical signs and symptoms that were present at baseline.
No response (meets 1 or more criteria)	
 • Death due to any cause; • Persistence of bacteremia based on blood cultures obtained through Day 7 or recurrence of SAB; • Development of new metastatic foci after Day 7 or other complications related to SA; or • Persistence, worsening, or recurrence of attributable signs and symptoms of SAB which were present at baseline.
Indeterminate	Study data not available for the evaluation of efficacy due to lost to follow-up, withdrawal of consent, or missing data.

SA = *Staphylococcus aureus*; SAB = *Staphylococcus aureus* bacteremia.

7.4 National Early Warning Score 2

Table 3 presents the NEWS2 scoring system. A NEWS2 score will be recorded once per day (and should be repeated if there is a change in clinical status) from Day 1 through Day 7 and TOC for study drug (Day 12). NEWS2 is an aggregate scoring system derived from 6 physiologic parameters:

- Respiration rate;
- Oxygen saturation;
- Systolic blood pressure;
- Pulse rate;

- Level of consciousness or new confusion; and

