8.9 Vital Signs

Vital signs will be measured at Screening, prior to infusion (-1 hour window) daily on Day 1 through Day 7, TOC for study drug (Day 12), TOC for BAT, and EOS. Vital signs will include temperature, heart rate, and blood pressure. Vital signs will be obtained at every visit unless the subject has been discharged and visits are being performed remotely. During the Treatment Period, vital signs should be obtained prior to each infusion (-1 hour window). Wherever possible, vital signs will be obtained after at least 5 minutes resting in a supine or sitting position. If more than 1 measurement is taken on a given day, the highest value for temperature should be recorded in the eCRF.

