**Table 3. Microbiological Outcome**

Category	Criteria
Eradication	Blood cultures negative for SA for 2 consecutive days.
Presumed eradication	Follow-up blood cultures were not done (or were technically uninterpretable) and the subject has responded clinically, as defined in Table 2 of protocol .
Persistence	Follow-up blood cultures do not meet the criteria for eradication and are positive for SA either daily or every other day.
Presumed persistence	Follow-up blood cultures were not done (or were technically uninterpretable) and the subject has not responded clinically, as defined in Table 2 of protocol .
Recurrence	A positive blood culture for SAB at any time after documented eradication or presumed eradication.

In [Table 3](#), “the subject has responded clinically” indicates that the subject experiences clinical improvement or response per investigator’s assessment at EOT for study drug. Any 2 consecutive assessments with blood cultures negative for SA is assigned as Eradication programmatically, no matter if these 2 assessments are consecutive days or consecutive visits.

Time to first resolution of any signs/symptoms related to focal site of SA infection (e.g., joint pain; redness; swelling; weight-bearing, back pain; weight-bearing, skin redness; drainage) from randomization on Day 1 will be analyzed. If all signs/symptoms are absent, the subjects will be considered achieving the resolution of signs/symptoms related to focal site of SA infection. If any signs/symptoms are present during the study assessments, the subjects will be censored at the date of latest assessment of signs/symptoms assessments for focal site of SA infection.

Time-to-event (days) = Censoring date/date of first resolution assessment – date of first dose of study drug + 1

The Kaplan-Meier method will be used to estimate the 25%, median and 75% times. The hazard ratio, 95% confidence interval (CI) of hazard ratio, and p-value from Cox regression model will be provided to compare AP-SA02 and placebo. Cox regression will include treatment (AP-SA02 and placebo) as factor. All assessments from scheduled and unscheduled visits will be included in the time-to-event analysis.

The Kaplan-Meier plot of time to first resolution of any signs/symptoms related to focal site of SA infection will be provided.

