If Day 12 blood culture is positive, the subject will not be considered have initial resolution of SAB although there may be 2 or more consecutive negative blood cultures before Day 12. If EOS or BAT blood culture is positive, the subject will be considered as initial resolution of SAB when there are 2 or more consecutive negative blood cultures before EOS or BAT, and the initial resolution date and time will be the first date and time with 2 consecutive negative blood cultures. The subjects who do not experience the resolution will be censored at the last collection date and time of blood culture.

- Time to initial resolution of SAB (days) = (Censoring date and time/first date and time of 2 consecutive days with negative SA blood culture – date and time of first dose of study drug) /3600/24

The Kaplan-Meier method will be used to estimate the 25%, median and 75% times. The hazard ratio, 95% confidence interval (CI) of hazard ratio, and p-value from Cox regression model will be provided to compare AP-SA02 and placebo. Cox regression will include treatment (AP-SA02 and placebo) as factor.

The Kaplan-Meier plot of time to initial resolution of SAB will be provided.

Time to resolution of any signs and/or symptoms of bacteremia present at Screening will be analyzed using the Kaplan-Meier method as other time-to-event endpoints.

- Time to resolution of signs/symptoms of bacteremia (days) = Censoring date/date of first resolution of any signs/symptoms of bacteremia - date of first dose of study drug + 1

The Kaplan-Meier method will be used to estimate the 25%, median and 75% times. The hazard ratio, 95% confidence interval (CI) of hazard ratio, and p-value from Cox regression model will be provided to compare AP-SA02 and placebo. Cox regression will include treatment (AP-SA02 and placebo) as factor.

The Kaplan-Meier plot of time to resolution of any signs and/or symptoms of bacteremia present at Screening will be provided.

The signs and symptoms of SAB will be determined programmatically based on the following:

- Documented temperature  $\geq 38.0^{\circ}\text{C}$  ( $100.4^{\circ}\text{F}$ ) or  $\leq 36.0^{\circ}\text{C}$  ( $96.8^{\circ}\text{F}$ ) measured orally,  $\geq 38.5^{\circ}\text{C}$  ( $101.3^{\circ}\text{F}$ ) or  $\leq 36.5^{\circ}\text{C}$  ( $97.7^{\circ}\text{F}$ ) measured tympanically, or  $\geq 39^{\circ}\text{C}$  ( $102.2^{\circ}\text{F}$ ) or  $\leq 37^{\circ}\text{C}$  ( $98.6^{\circ}\text{F}$ ) measured rectally;

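### SAP 3.4.1 gives the focal-sign endpoint overlapping event and censoring rules, SAP 3.6 leaves resolution of bacteremia signs undefined, and neither requires resolution to last

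*SAP*

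**What the plan says.** **Focal signs (SAP 3.4.1, text after Table 3).** The event rule is: "If all signs/symptoms are absent, the subjects will be considered achieving the resolution". The next sentence is the censoring rule: "If any signs/symptoms are present during the study assessments, the subjects will be censored at the date of latest assessment". Time runs to the first assessment that shows resolution. Focal signs are assessed at Screening, daily on Days 1 to 7, on Day 12, at TOC for BAT and at EOS (SAP Appendix A, note u).

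**Bacteremia signs (SAP 3.6).** Protocol 7.2 names the endpoint "Time to resolution of any signs and/or symptoms of bacteremia present at Screening". The SAP ends the clock at the "date of first resolution of any signs/symptoms of bacteremia". On method it says only that the endpoint "will be analyzed using the Kaplan-Meier method as other time-to-event endpoints". It then says "The signs and symptoms of SAB will be determined programmatically based on the following" and lists six categories: temperature, heart rate, respiratory rate, white cell count, systolic pressure and focal pain. It does not say how many must be absent, for how long, or when a subject is censored.

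**Related rules.** For clinical response, Protocol Table 2 requires "Resolution of SAB-related clinical signs and symptoms that were present at baseline" and counts recurrence of such signs as no response. SAP Table 2 requires NEWS2 to be at or below 2 on 2 consecutive days. SAP 3.6 requires 2 consecutive days of negative cultures, and a positive Day 12 culture cancels the resolution.

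Both sign endpoints receive Kaplan-Meier quartiles, a Cox hazard ratio with its interval, and a p-value. SAP 3.1.4 states that there is no formal testing.

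**The concern.** A programmer could not derive either endpoint from the SAP without guessing, and the guess decides who has an event and when.

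For focal signs, an ordinary recovery (signs early, none later) satisfies the event rule and the censoring rule, and no precedence is given. Read literally, the censoring rule removes the recoveries that the endpoint is meant to time.

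For bacteremia signs, the literal text lets a single sign end follow-up while the others persist. The cross-reference to other time-to-event endpoints does not settle censoring, because those endpoints use different dates: last visit (NEWS2, hospital discharge), last sign assessment (focal signs), last date known alive (death) and last culture (resolution of SAB).

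For both, a brief normal spell counts as resolution, unlike in the NEWS2 and culture endpoints. At stake is whether two sets of reported times and hazard ratios describe recovery or fluctuation.

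**Working it through.** **1. The plan's own figure.** None is given for either sign endpoint. The only design calculation is for Clinical Improvement at Day 12: 80% against 30%, 38 subjects at 2:1, one-sided Fisher test at 0.05. Exact enumeration gives 87.8% power (25:13) or 86.3% (26:12), so the stated minimum of 80% holds. It does not involve these endpoints.

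**2. Focal rules applied to one subject.** Take joint pain on Days 1 to 4, none from Day 5, followed to EOS. SAP time = date minus first-dose date plus 1.

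| Rule applied | Status | Time (days) |
|---|---|---|
| All signs absent | Event on Day 5 | 5 |
| Any sign present on study | Censored at last assessment, EOS | nominally 39 to 81 |

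If the censoring rule prevails, the only events left are subjects with no focal sign at any on-study assessment. No restriction to subjects with a focal sign at baseline is stated, so a subject who never had one would count as resolved on Day 1.

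**3. One sign against all signs (SAP 3.6).** Assume that each baseline sign resolves for good after an independent exponential time with mean 5 days, seen at the next assessment (Days 1 to 7, then 12).

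- First of k signs: median = (5/k) × ln 2. For k = 2 this is 1.73, seen on Day 2. For k = 3 it is 1.16, seen on Day 2.
- Last of k signs: median = −5 × ln(1 − 0.5^(1/k)). For k = 2 this is 6.14, seen on Day 7. For k = 3 it is 7.89, seen on Day 12.

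The reading of *any* therefore moves the median from Day 2 to Day 7 (two signs) or Day 12 (three signs).

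**4. Persistence.** Take a subject who never recovers. Assume each of k signs is absent by chance at an assessment with probability q, independently, over the 8 assessments through Day 12.

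- Any sign absent once: 1 − (1 − q)^(8k)
- All signs absent once: 1 − (1 − q^k)^8
- All signs absent at 2 consecutive assessments: run calculation with daily probability q^k

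| k | q | Any, once | All, once | All, 2 consecutive |
|---|---|---|---|---|
| 2 | 0.1 | 81.5% | 7.7% | 0.1% |
| 2 | 0.2 | 97.2% | 27.9% | 1.1% |
| 2 | 0.3 | 99.7% | 53.0% | 5.2% |
| 3 | 0.1 | 92.0% | 0.8% | <0.1% |
| 3 | 0.2 | 99.5% | 6.2% | <0.1% |
| 3 | 0.3 | >99.9% | 19.7% | 0.5% |

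Requiring all signs to be absent removes most false resolutions when q is small or there are three signs. With two fluctuating signs, up to about half remain unless absence must be seen twice. Neither q nor the recovery time comes from the documents.

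**5. How strict a persistence rule can be.** Protocol 8.9 has vital signs taken before each infusion, four a day on the 6-hourly schedule. Suppose every reading on 2 consecutive days (8 readings) had to be at or below 90/min. For a recovered subject with assumed mean heart rate 85 and independent readings, p = Φ((90.5 − 85)/SD):

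- SD 5: p = 0.864, p^8 = 0.31
- SD 8: p = 0.754, p^8 = 0.10

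Such a rule would fail 69% to 90% of recovered subjects on a given pair of days, so it is too strict.

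**The case against.** **The one-sign reading is not the only one.** SAP 3.4.1 also titles its focal endpoint as first resolution of *any* signs, and then defines that as all absent. By analogy, *any* in SAP 3.6 may mean whatever signs were present at Screening. This stands: the documents do not show that one sign was meant to suffice. But SAP 3.6 omits the clarifying sentence, so the ambiguity remains.

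**The focal censoring sentence is loose drafting.** It follows an event definition, and the formula uses a first resolution date, so it probably covers subjects who never resolve. That is the likely intent, but it is not what the sentence says. A reader might infer that both endpoints censor true recoveries. They do not: the conflict is confined to focal signs, and the bacteremia endpoint simply lacks a censoring rule of its own.

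**Time to first resolution is a legitimate endpoint.** Durability is partly covered by clinical response at Day 12, TOC for BAT and EOS, where recurrence counts as no response. This stands in part. Requiring persistence is partly a choice of endpoint, though the choice should be stated.

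**Heart-rate noise proves little.** With an assumed mean of 95/min, SD 5 to 8 and four independent readings, the chance of at least one reading at or below 90 in a day is 56% to 74%. A reader might take this as a false-event rate. It is not: it assumes a single sign, independent readings and an any-reading rule that the SAP does not state. Protocol 8.9 also has the highest temperature of the day recorded, so for that sign one normal reading among febrile ones cannot score. Correlation between readings would lower the figure.

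**Conclusion.** The point holds as a defect in how two endpoints are defined. The overlap of the focal rules, the missing all-absent sentence, the absent censoring rule for bacteremia signs and the silence on duration are visible in the text and need no assumptions. If programmed literally, the rules give wrong event times: a Day 5 focal recovery becomes a censored observation at EOS, and a bacteremia-sign time can stop when the first of several signs normalises.

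The sizes in the tables are illustrations that rest on assumed independence, fluctuation rates and recovery times. They show that the definition matters; they do not estimate an error in this trial.

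The consequence is limited to the Kaplan-Meier times, hazard ratios and nominal p-values of two endpoints in a long unranked list. Power and type 1 error are untouched. A reader might also infer that the hazard ratios are pulled toward 1. Misclassification that is equal in both arms would mostly dilute a difference, but no hazard ratio was computed and the direction is not established.

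This should be corrected before database lock, but it does not threaten the trial's main conclusions.

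**What to change.** Amend SAP 3.4.1 and 3.6 before database lock:

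1. **Bacteremia event.** Define it as all signs and symptoms present at Screening being absent on the same assessment day, using one prespecified value per sign per day. State which white cell value counts on Day 6, when the schedule has no laboratory sample.
2. **Censoring.** Replace the focal sentence with a rule that only subjects who do not reach resolution are censored, at their last sign or symptom assessment. Use the same rule for the bacteremia endpoint.
3. **Who is analysed.** Limit each analysis to subjects with at least one relevant sign at baseline.
4. **Persistence.** Add a version requiring absence at 2 consecutive assessments, dated to the first, either as a sensitivity analysis or as the main definition. Do not require every pre-infusion reading to be normal. Say how pairs that span the gap from Day 7 to Day 12, or from Day 12 to TOC for BAT, are treated.

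The cost is SAP wording and programming on data already collected. The downside is somewhat fewer and later events.

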7.10 Pharmacodynamic Assessments

Pharmacodynamics will be evaluated based on the following:

- Time to resolution of signs/symptoms of bacteremia present at Screening;
- Time to resolution of bacteremia based on blood cultures; and/or
- Change in CRP from baseline.

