### 2.2.4 Sample Size Determination

The study will enroll approximately 50 eligible subjects. Enrollment may be expanded up to a total of approximately 100 subjects to ensure that at least 8 treated and 4 placebo Phase 2a subjects are MRSA subjects and to account for additional subjects and cohorts that may be enrolled based on DRC review and Sponsor input based on emerging data. To ensure that at least 8 treated and 4 placebo Phase 2a subjects are MRSA subjects, no more than approximately 70 non-MRSA subjects will be enrolled without a protocol amendment.

The Phase 1b MAD safety cohorts will follow a standard 3 + 1 design for 2 cohorts (n = 4 for each cohort for a total of 8 subjects). However, additional cohorts (up to 3) may be added or existing cohorts expanded per recommendation of the DRC or Sponsor decision. The total sample size in Phase 1b may be increased up to a total of 20 subjects without a protocol amendment in consultation with the DRC.

Phase 2a will have an initial sample size of approximately n = 42 with a study drug to placebo allocation of 2:1 in order to enroll at least 38 subjects meeting the Microbiological Intent-to-Treat (MITT) Population criteria with the assumption that approximately 90% of randomized subjects will satisfy the MITT Population criteria. This will provide at least 80% power to detect a difference of 50% in the proportion of subjects in each treatment arm, with a 30% placebo portion meeting all conditions for Clinical Improvement or response at TOC for study drug (Day 12) in the MITT Population with a type 1 error rate of 0.05 (1-sided) using Fisher's exact test. Additional subjects may be included in Phase 2a after a protocol amendment.

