- TEAEs, which are defined as AEs occurring after the first dose of study drug through TOC for study drug (Day 12) or through EOS for SAEs
- Proportion of subjects with acute kidney injury (AKI), defined as stage 1 or higher using modified Risk-Injury-Failure-Loss-End-stage renal disease (RIFLE) criteria at any time within the first 7 days or new need for renal replacement therapy between Day 1 and EOS
- Vital signs
- Clinical laboratory evaluations
- Change in C-reactive protein (CRP) from baseline to EOS
- Change in interleukin-10 from baseline through TOC for study drug (Day 12)
- Change in SA isolate sensitivity to AP-SA02 between initiation of study drug and the last isolation of SA from a sterile site (blood, joint fluid, tissue)
- Change in SA isolate susceptibilities to anti-staphylococcal antibiotics from baseline
- Change in SA isolate susceptibility to BAT from baseline; and
- Clinical and microbiological outcomes by foci of infection.

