- Heart rate  $>90$  beats per minute;
- Respiratory rate  $>20$  breaths per minute;
- White blood cell count  $\geq 12.0 \times 10^9$  cells/L or  $\leq 0.4 \times 10^9$  cells/L, or  $\geq 10\%$  immature neutrophils;
- Systolic blood pressure  $<90$  mmHg; and/or
- Pain associated with focal site of infection.

CRP and Interleukin-10 results will be summarized with descriptive statistics at baseline, each scheduled post-baseline visits. Changes from baseline for each scheduled post-baseline visit, the minimum, maximum, last post-baseline value. Both scheduled and unscheduled post-baseline values will be considered for the summaries. A paired t-test p-value will be used to compare the baseline value with each scheduled post-baseline values. An unpaired t-test p-value will be used for the change from baseline at each scheduled study day to compare AP-SA02 and placebo.

Changes from baseline will be plotted by AP-SA02 and placebo at each scheduled study day for each subject.

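### CRP and IL-10 are compared on raw change without baseline adjustment, which can cost much of the power to show a proportional effect; log-scale ANCOVA is a cheap improvement

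*SAP*

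**What the plan says.** SAP 3.6 gives the whole analysis of the two markers in one paragraph. It begins "CRP and Interleukin-10 results will be summarized with descriptive statistics at baseline, each scheduled post-baseline visits" and adds "Changes from baseline for each scheduled post-baseline visit, the minimum, maximum, last post-baseline value". Two tests follow. Within arm: "A paired t-test p-value will be used to compare the baseline value with each scheduled post-baseline values". Between arms: "An unpaired t-test p-value will be used for the change from baseline at each scheduled study day to compare AP-SA02 and placebo". Each subject's change is also plotted.

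Neither document names a log scale, a ratio to baseline, a baseline covariate or a rank test for these markers. The paragraph names no confidence interval, although Protocol 9.2.1 promises 95% intervals for the Phase 2a endpoints.

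Protocol 7.10 lists "Change in CRP from baseline" as one of three pharmacodynamic measures. SAP 2.3.2 lists "Change in C-reactive protein (CRP) from baseline to EOS" among the Phase 2a endpoints, and the IL-10 change through Day 12 as another. SAP 3.1.4 states that no formal testing will be done, so the p-values are nominal.

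**The concern.** CRP and IL-10 are positive concentrations. If they fall roughly in proportion as infection resolves, a subject with a high baseline shows a large absolute fall in either arm. Two things then weaken a t-test on the raw change:

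- The spread of the baselines enters the noise in full, because nothing adjusts for it.
- A proportional drug effect shrinks in absolute units as the placebo arm falls. All subjects receive background antibiotics, and the CRP endpoint runs to 28 days after these end. A substantial placebo fall by then is likely, but that is an inference, because the documents give no marker values.

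At stake is how two exploratory markers are read in a first-in-human trial. A large p-value at every visit may be taken as absence of a pharmacodynamic effect when the chosen statistic had little chance of showing one.

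**Working it through.** **The plan's own figure.** The only power statement in the documents (SAP 2.2.4) concerns Day 12 clinical response: at least 80% for 30% versus 80%, Fisher's exact test, one-sided 0.05. The sample is set "in order to enroll at least 38 subjects meeting the Microbiological Intent-to-Treat (MITT) Population criteria". Since 42 × 0.9 = 37.8, about 38, the 2:1 split is about 25:13. Exact enumeration at 25:13 gives 87.8%, so the statement holds. It says nothing about CRP or IL-10.

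**Inputs.** From the documents: 25:13, and an unpaired t-test on change. Assumed: lognormal values with the same CV at both times, log-scale correlation 0.5, two-sided 5%, pooled variance, a true halving (active/placebo ratio 0.5), baseline median 150 and placebo post-baseline median 60 (40% of baseline) in arbitrary units. Only the ratios matter.

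**Formulas.** Log-scale SD s = √ln(1 + CV²). Standard error factor √(1/25 + 1/13) = 0.342. Approximate power = Φ(difference/SE − 1.96).

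**By hand at CV 50%** (s = √0.2231 = 0.472; mean = median × 1.118):

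- *Raw change, placebo at 40%.* The means are 67.1 and 33.5, a difference of 33.5. SDs are 83.9 (baseline), 33.5 (placebo post) and 16.8 (active post). The raw-scale correlation is (e^0.1116 − 1)/0.25 = 0.472. The SD of change is 74.2 on placebo and 77.4 on active, pooled 76.3. SE = 76.3 × 0.342 = 26.1. The ratio is 1.29, so power is about 25%.
- *Raw change, no placebo decline.* The difference is 167.7 − 83.9 = 83.9. The pooled SD of change is 78.2, SE 26.7. The ratio is 3.13, so power is about 88%.
- *Log ratio.* SD = s√(2(1 − 0.5)) = 0.472. Then 0.693/(0.472 × 0.342) = 4.29, so power is about 99%, whatever the placebo decline.
- *Log ANCOVA.* Residual SD = s√(1 − 0.5²) = 0.409. The ratio is 4.95, so power is above 99%.

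The noise of the raw change is nearly the same in the first two lines (76 and 78) and close to the baseline SD of 84. What differs is the absolute effect, 33.5 against 83.9.

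**Simulation, halving, placebo at 40% of baseline** (a repeat run agreed within about 2 points):

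| CV | Raw change | Log ratio | Raw ANCOVA | Log ANCOVA |
|---|---|---|---|---|
| 30% | 57% | 100% | 100% | 100% |
| 50% | 25% | 98% | 99% | 100% |
| 70% | 17% | 88% | 91% | 95% |
| 100% | 11% | 66% | 69% | 79% |
| 200% | 6% | 35% | about 30% | 44% |

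**Placebo decline varied, CV 50%, raw change:** about 87% with no decline, 62% at 70% of baseline, 25% at 40%, and 9% at 20%. At CV 100% with no decline it is about 37%.

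**Smaller effect.** For a 30% reduction with placebo at 40%, raw change versus log ratio is about 12% versus 57% at CV 50%, and 6% versus 23% at CV 100%.

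**Under no effect**, all tests reject in about 4–5% of trials.

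**A second data model** (post = baseline × fraction × effect × noise; baseline log-SD 0.5–1.2, log-ratio SD 0.5–1.0, placebo at 100% to 20% of baseline; 80 scenarios). The log ratio had more power than the raw change in every scenario. Raw power was below 50% in 68 of 80, and in 47 of 48 once placebo fell to half or lower. With log-ratio SD 0.7 and placebo at 30–70% of baseline, the top quarter of baselines supplied 63–65% of the sum of squares of the raw change at baseline log-SD 0.5, and 87–91% at 1.0. In this model log ANCOVA was about one point below the log ratio.

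**The case against.** **The inputs are assumed.** This stands. A reader might infer that a halving would mostly be missed as planned, while a log analysis would usually find it. The documents do not support that as a flat statement, because they give no variance, level or effect. It fails with mild skew and little placebo decline: in the second model, raw power is 60–91% at baseline log-SD 0.5, log-ratio SD 0.5–0.7 and placebo at 70–100% of baseline. It also fails with very large spread, where the log ratio reaches only 44% at CV 150% and 35% at CV 200%.

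**The scale is not the main culprit.** This stands too. A reader might infer that untransformed values as such discard the information. The raw ANCOVA column shows otherwise: with raw baseline as covariate and no logs, nearly all the loss is recovered up to a CV of 100%. The damage comes mainly from subtracting an unadjusted baseline. The log scale adds a further gain when the data are skewed.

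**Values below the assay limit could hurt a log analysis.** This stands in part. With a limit of 50 in the scenario above, so that the active median of 30 lies below it, and half-limit substitution, log-ratio power falls from 88% to 64% at CV 70% and from 65% to 37% at CV 100%. Raw ANCOVA gives 83% and 60%. The documents state no limit, so no substitution rule should be fixed blind.

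**The stakes are small, and absolute change is a legitimate quantity.** This stands. The p-values are nominal, medians and ranges are reported, and individual changes are plotted. Late in follow-up, a halved low CRP really is a small absolute difference. None of this gives the reader an efficient between-arm estimate.

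**Conclusion.** The point holds as a low-stakes improvement. The planned comparison of CRP and IL-10 had less power than the log ratio in every alternative scenario run, by an amount that depends on skew and on how far placebo falls. Under the stated assumptions, with placebo at 40% of baseline, raw change has about 57% power at CV 30% and 11% at CV 100%, against 100% and 79% for log ANCOVA. With no placebo decline and CV 50%, raw change still reaches about 87%. The error is toward missed effects, not false positives. It cannot be said from the documents that a real effect on either marker will usually be reported as no difference, since that depends on figures they do not contain.

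**What to change.** In SAP 3.6, replace the unpaired t-test for CRP and IL-10 with a linear model at each scheduled visit: log post-baseline value as outcome, log baseline as covariate, treatment as factor. The log ratio to baseline, compared by t-test, is the simpler alternative. Report the between-arm geometric mean ratio with its 95% CI at each visit, which also supplies the interval that Protocol 9.2.1 promises. Keep raw medians, ranges and subject plots as descriptive output. State how values below the quantification limit are handled once the assay limit and the fraction below it are known, before unblinding, and do not fix half the limit now.

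The cost is a few SAP sentences and a small change to the program, with no new data. The downside is that results read as ratios, not absolute units.
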